Endotoxin Administration (Main Study Session): The main study session including endotoxin administration and experimental tasks will be conducted at the UCLA Clinical & Translational Research Center (CTRC). Participants will arrive at the CTRC at 07:00. Upon arrival, a urine sample will be collected and tested for drug use and pregnancy in order to ensure continued eligibility for study participation. A CTRC nurse will assess vital signs (blood pressure, pulse, temperature). An indwelling venous catheter with a heparin lock will be inserted into the participant's dominant forearm for hourly blood draws and one into the non-dominant forearm for endotoxin administration. Oral hydration with water or juice will be offered hourly in order to minimize the negative side effects of endotoxin (hydration reduces risk of diastolic blood pressure decreases). Following these procedures, participants will eat a light breakfast before undergoing experimental tasks and taking the last dose of study drug at 08:30. At 09:00 (T_0), participants will receive endotoxin (0.8 ng/kg of body weight) or IV placebo as an intravenous bolus over 30-60 seconds. Endotoxin to be used in this study is derived from *Escherichia coli* (*E. coli* group O:113) and will be provided by the NIH Clinical Center.⁹¹

Safety Monitoring and Discharge from Study: Participants will be monitored as per the protocol (see Protections of Human Subjects section) and discharged following the last blood draw upon approval from the study physician. Briefly, in addition to the continuous observation, scheduled nursing assessments including vital sign check will be performed every 30 minutes for the first 2 hours after LPS administration and then hourly. If any potential adverse reactions are noted as detailed in the protocol, the study physician will be contacted and the pre-determined actions will be taken as appropriate such as ECG, verbal or manual stimulation, relieving medications, or discontinuation of the study procedures.

C.2.4. Baseline Measures (Prior to Pretreatment): During the in-person screening session, the following measures will be assessed: sociodemographic information, sleep (DSM-5 insomnia using the SCID-5⁹² and sleep disturbance using the Pittsburgh Sleep Quality Index⁹³), depressive/anxiety symptoms (Inventory of Depressive Symptomatology⁹⁴, Beck Depression Inventory⁹⁵, Beck Anxiety Inventory⁹⁶, POMS⁶⁷, and the Montgomery-Asberg Depression Rating Scale [MADRS]⁹⁷), cognitive functions (estimated IQ using Test of Premorbid Functioning from Advanced Clinical Solutions™; verbal memory, visual memory, executive function, and attention using computerized tests from CNS Vital Signs™ including Verbal Memory Test, Visual Memory Test, Stroop Test, Shifting Attention Test, and Continuous Performance Test), systemic inflammation (CRP), and kynurenone metabolism (TRP, KYN, 3HK, QA, and KynA). Baseline measures such as sex, sleep disturbance, systemic inflammation, and KYN metabolism will be tested as potential moderators of the pretreatment effects on endotoxin-induced depression outcomes. In particular, we expect stronger effects of leucine pretreatment in females compared to males because our previous studies indicate that: 1) whereas

endotoxin increases circulating proinflammatory cytokines and IDO activity (i.e., KYN/TRP ratio) equally in males and females,^{22,53} it increases depressed mood much more robustly in females²²; 2) the correlations between cytokines and depressed mood are stronger in females²²; and 3) the correlations between IDO activity and depressed mood are stronger in females⁵³. Furthermore, before and after pretreatment, blood samples will be drawn for the assays of intracytoplasmic cytokine expression (IL-1, IL-6 and TNF- α) and nuclear signaling of inflammation (nuclear factor [NF]- κ B) using ex-vivo stimulation with endotoxin (also known as lipopolysaccharide [LPS] stimulation). These assays will measure the cellular production of cytokines in response to LPS stimulation and thus the sensitivity of peripheral blood mononuclear cells (PBMC) to an inflammatory challenge before and after pretreatment.

C.2.5. Repeated Measures (Main Study Session)

Behavioral Measures: Depressed mood, a core symptom of depression, will be assessed immediately before endotoxin administration (T_0) and then hourly for the next 6 hours (T_1-T_6) using the POMS⁶⁷ (primary outcome). We will also use the MADRS⁹⁷ hourly (T_0-T_6) as it is sensitive to acute changes in depressed mood and anhedonia following endotoxin¹⁹ and is less oriented towards somatic symptoms than the Hamilton Depression Rating Scale. Because feelings of social disconnection and loneliness predict depression and co-occur with depressed mood following inflammatory challenge, feelings of social disconnection (Feelings of Social Disconnection Scale²¹) and loneliness (adapted UCLA Loneliness Scale⁹⁸) will also be assessed.

Participants will also complete self-report measures of sickness symptoms (e.g., muscle pain, fatigue).

Cognitive Measures: Three items from the POMS-Confusion subscale (unable to concentrate, forgetful, confused) will be assessed at T_0 and then hourly (T_1-T_6).⁶⁷ Verbal memory, visual memory, executive function, and attention be assessed at T_0 and then between T_2 and T_3 using computerized tests from CNS Vital Signs™: Verbal Memory Test, Visual Memory Test, Stroop Test, Shifting Attention Test, and Continuous Performance Test. Reichenberg et al. assessed cognitive impairment at 1, 3, and 9 hours after endotoxin and found it to be worst at 3 hours.²⁰ The order of tests will be counterbalanced across subjects to avoid any non-random version-dependent bias.⁹⁹

Cytokines, Kynurenone Metabolites & Gene Expression Analysis: Blood samples will be collected immediately before endotoxin administration (T_0) and then hourly (T_1-T_6). Samples will then be appropriately processed and stored for later assessment of proinflammatory cytokines (IL-1 receptor antagonist, IL-6, TNF- α , soluble TNF receptor) and KYN metabolites (TRP, KYN, 3HK, QA, KynA). Depressed mood and biomarkers will be hourly assessed even after the time of peak responses (T_2) because depressed mood can linger and has been shown to correlate with cytokines and kynurenone metabolites.^{16,42} At baseline prior to pretreatment, immediately before endotoxin injection (T_0), and 30 minutes post-injection ($T_{0.5}$), blood samples will be drawn in PaxGene RNA tubes, which preserve RNA integrity. Genome-wide transcriptional profiling will be conducted using Illumina HT-12 BeadArrays. Gene expression analysis will provide information on the underlying biological mechanisms of inflammatory and affective responses, and in particular, will be used to independently replicate the findings of our prior endotoxin studies.

C.2.6. Experimental Tasks (Main Study Session)

For Negative Affect: **Subjective Sensitivity to Social Rejection (Cyberball Social Exclusion Task):** Feelings of 'social disconnection' play a critical role in the onset and perpetuation of (non-inflammatory forms of) depression.¹⁰⁰ Inflammatory processes can trigger social withdrawal¹⁰¹ and increase feelings of distress and related neural sensitivity (i.e., activation of the dorsal anterior cingulate cortex).²¹ Using the Cyberball Social Exclusion Task,¹⁰² we will examine feelings of social distress. Participants will be told that they will play a virtual ball-tossing game with two other players over the Internet. In reality, they will play with a preset computer program. In the first round (inclusion), participants will play with the two other players for the entire period. In the second round (exclusion), participants will receive the ball for 7 throws and then will be excluded for the rest of the round when the two players will stop throwing the ball to the participant. Following this task, they will complete a measure of social distress in response to social exclusion.¹⁰³

Negative Bias in Facial Emotion Recognition (Emotional Face Recognition Task): Depressed subjects have a negative bias in the perception of emotions expressed in faces as they tend to interpret neutral faces as sad and happy faces as neutral.⁷⁶ Furthermore, such a bias appears to play a role in the etiology and maintenance of depression as it predicts relapse in currently depressed and remitted patients.⁷⁷ Emotional Face Recognition Task¹⁰⁴ consists in showing participants a series of black and white photographs (Ekman Pictures of facial affect), in which the facial expression is morphed from neutral to either Sad, Angry, or Happy.¹⁰⁵ For each image, participants will be asked to make a forced choice about the emotion expressed, and rate their certainty on a 0-9 scale. Earlier recognition of a Sad face with certainty would be indicative of negative bias.

For Positive Affect: Subjective Sensitivity to Social Acceptance (Positive Social Feedback Task): Decreased sensitivity to positive social experiences, like social acceptance, is another mechanism that might account for cytokine-induced feelings of social disconnection and depressed mood. The Positive Social Feedback Task was developed based on Izuma et al.'s study involving monetary and social rewards, which demonstrated that positive social feedback robustly activates reward-related brain areas, notably the striatum, and these overlap with the areas activated by monetary rewards.¹⁰⁶ Prior to the experimental session, participants will be asked to complete a survey that contains several personality questionnaires (NEO Five Factor Inventory),¹⁰⁷ as well as several open-ended questions ("What do you do in your free time?" "Briefly describe your personality." "What is your main goal in the future?"). Then, participants will be video-recorded for 2-5 minutes as they discuss what they like about themselves. Participants will be told that 8 people (4 male, 4 female) will form impressions of them—based on their answers to the personality questionnaires and the video-taped self-introduction—by selecting personality traits to describe them. Participants will then see a photograph of themselves along with a descriptive word underneath (supposedly provided by the evaluators), which will be pre-rated based on desirability, and will be asked to rate subjective happiness when each of the feedback items is presented, using a 7-point scale.

Reward (Reward Learning Task): Anhedonia is a core feature of major depressive disorder and includes a reduction in experienced pleasure (liking reward) and dysfunction in reward anticipation reward learning.⁷⁸⁻⁸⁰ We have found that inflammatory challenge reduces neural sensitivity to reward anticipation.¹⁰⁸ We will use a laboratory based probabilistic reward task that objectively measures participants' ability to modulate behavior as a function of reward, because this task identifies reduced reward learning in depressed patients which is state-dependent and also predicts the persistent diagnosis of depression in the midst of treatment.⁷⁸⁻⁸⁰ This computerized reward-learning task is extensively described in Pizzagalli et al.¹⁰⁹

Order and Timing of Experimental Tasks: The order of the tasks will be first a randomized sequence of Reward Learning and Emotional Face Recognition, then followed by a randomized sequence of Positive Social Feedback and Cyberball Social Exclusion. Because the latter two tasks involve deception, they will be completed only once after the former two tasks, at T₂, time of peak cytokine responses. The former two tasks will be completed at T₀ and T₂.

C.2.7. Interpretation of Results and Potential Pitfalls

As leucine may not inhibit endotoxin-induced inflammation, unopposed sickness symptoms could mask the antidepressant effects of leucine assessed using the POMS. Thus, the results will be statistically adjusted for sickness symptoms. Furthermore, we will use experimental tasks of negative and positive affect to assess mood-specific processes. Although the proposed leucine dose is above average,^{30,87} the adequate antidepressant dose is unknown. Thus, if an interim data analysis for the first 30 participants using 12 g/day shows no signal of an antidepressant effect, we will consider increasing the dose to 16 g/day for the same period of 14 days. Of note, 16 g/day was the maximum dose of leucine used in long-term supplementation studies according to a meta-analysis.³⁰

C.2.8. Statistical Analysis

The basic design is a 2 group (leucine vs. PO placebo) by 2 condition (endotoxin vs. IV placebo) independent analysis of variance (ANOVA) with one or more repeated outcome measures analyzed with linear mixed models (LMM) with primary focus upon the two endotoxin-exposed groups. The number of repeated measures varies by assessment. The key results are the main effects of pretreatment (i.e., group) while the main effects of group, condition, and their interaction will be tested. For analyses with repeated measures, the two main effects and interaction will further interact with the time variable. POMS will be the primary outcome measure. Simes correction for multiple testing will be applied for the secondary outcome measures as they are expected to be correlated.¹¹⁰

C.2.9. Justification of Sample Size

The effect sizes for the reduction of endotoxin-induced depressive symptoms by leucine within the animal data are very large ($d=.90$), but we have assumed some attenuation in humans ($d=.70$). Assuming an effect of this size, with $n=35$ per group, there is >80% power to detect differences between the leucine and PO placebo pretreatments with endotoxin exposure for the single time point outcomes (e.g., Cyberball Social Exclusion); comparisons for repeated measures assessments will have more power (>90%) and able to detect more subtle effects at >80% power. Both 'leucine + IV placebo' and 'PO placebo + IV placebo' arms are expected to show minimal depression with means over time to be very near zero but exist as reference points to the endotoxin condition, which our previous work suggests to have large effects. With repeated measures, $n=10$ can detect

medium sized effects ($d=.50$) with power $>80\%$. Thus, there is more than adequate power with 35 vs. 10 to show the effect of endotoxin exposure within pretreatment groups.

REFERENCES

3. Depression Guideline Panel: Clinical Practice Guideline 5: Depression in Primary Care, vol 2: Treatment of Major Depression. In: US Department of Health and Human Services PHS, Agency for Health Care Policy and Research, ed. Rockville, MD. 1993.

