A.7. Transient Cognitive Impairment in Endotoxin Model of Depression: Cognitive impairment is a common symptom of depression, experienced by two-thirds of depressed patients and associated with poor treatment response, but often overlooked by clinicians.³⁶ Low-dose endotoxin transiently impairs verbal and nonverbal memory functions in humans.²⁰ Independent preclinical data demonstrate that peripherally administered endotoxin induces memory deficit through IDO-dependent neurotoxic kynureneine metabolism; furthermore, a single peripheral injection of KYN is sufficient to induce memory deficit.⁶⁸ Notably, human studies have shown that the supplementation with branched-chain amino acids (leucine, isoleucine, and valine) has protective effects against cognitive deficits during strenuous exercises.⁶⁹⁻⁷² Based on the evidence from animal and human research, it is expected that the blockade of the BBB transport of KYN by leucine pretreatment will attenuate endotoxin-induced cognitive impairment.

A.8. Potential Impact of the Current Study and Future Directions: If the hypotheses are confirmed, the involvement of the kynureneine pathway in the induction of depressive symptoms, including cognitive impairment, will be demonstrated for the first time in a human experimental study. Furthermore, this proof-of-concept study will provide instrumental information in designing future trials of leucine to treat or prevent inflammation-associated depression. Given the minimal adverse effects and the additional benefits such as muscle mass preservation, leucine will be a prime candidate for a pharmacologic strategy to treat or prevent inflammation-associated depression.

B. INNOVATION

B.1. A highly controlled experimental model of depression to examine a novel mood mechanism

Low-dose endotoxin administration is a highly innovative experimental model to understand the causal role of inflammation in the induction of depressive symptoms; yet, it is a procedure that has only been implemented by a few laboratories in the world with only a small number of studies conducted to date (n=12).^{19,73} Using this experimental model, in addition to a randomized controlled trial design, we will evaluate the kynureneine pathway, beyond the inflammatory cascade, as a potential mechanism of inflammation-associated depression. To our knowledge, this will be the first human experimental study to evaluate the involvement of the kynureneine pathway in the induction of depressive symptoms.

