C.1.3. Endotoxin induces changes in KYN metabolism, which correlates with depressed mood

[figure not shown]

Fig. 5 Leucine reduces brain KYN:TRP ratios and blocks depression-like behavior. **A,B** Mean sucrose preference (%) and time spent immobile in the forced swim test (s) (\pm SEM) of mice treated with leucine or vehicle immediately before and 6 h after LPS or phosphate-buffered saline (PBS) ($n > 14$ per group). **C,D** Mean KYN:TRP ratios in plasma and brains (\pm 442 SEM) of mice treated with 50 mg/kg leucine or vehicle immediately before and 6 h after LPS or PBS ($n = 5$ per group).

** $p < 0.01$, *** $p < 0.001$ for LPS vs. PBS main effects. * $p < 0.05$, ** $p < 0.01$, *** $p < 0.001$ for leucine vs. vehicle main effects.

Aim: In the aforementioned study in C.1.2. (N=115), we examined whether endotoxin induces changes in kynurenine metabolism and whether these changes correlate with inflammation-induced depressed mood.

Methods: Circulating kynurenine metabolites (TRP, KYN, QA, KynA) were measured at T₀, T₂, and T₆. The primary outcome was IDO activity assessed using KYN/TRP. **Results:** Participants exposed to endotoxin (vs. placebo) showed greater increases in IDO activity (p<0.0001). Among endotoxin-exposed participants (N=61; 38 females), the correlation between IDO activity and depressed mood was highly significant (p=0.004).

Conclusion: Inflammatory challenge increased IDO activity, which in turn was significantly correlated with inflammation-induced depressed mood. *These data confirm endotoxin-induced increases in peripheral conversion of TRP to KYN as well as increases in depressed mood, and thus show the feasibility of inhibiting blood-to-brain transport of KYN as well as inflammation-induced depressed mood.*

C.2. Research Design and Methods

C.2.1. Overview of Study Design (Fig. 6):

In this double-blind randomized placebo-controlled four-arm study, a total of 90 healthy volunteers (ages 18-65) will be randomly assigned to a two-week pretreatment of L-leucine (hereafter referred to as leucine) or PO placebo (i.e., maltodextrin). After the pre-treatment period, they will receive low-dose endotoxin or IV placebo (i.e. saline): n₁=35 leucine + endotoxin; n₂=35 PO placebo + endotoxin; n₃=10 leucine + IV placebo; n₄=10 PO placebo + IV placebo. (see Justification of Sample Size for the rationale for smaller IV placebo arms)

[figure not shown]

Fig. 6 Overview of study design

C.2.2. Subjects:

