Participants will be recruited from: 1) flyers that will be posted at the UCLA campus including the UCLA Medical Center; 2) advertisements posted in local university and community newspapers and websites (Daily Bruin, Brentwood News, Santa Monica Daily Press, www.bruinwalk.com and www.dailbruin.com); and 3) lists of telephone numbers and mailing addresses purchased from GENESYS Sampling Systems (Fort Washington, PA), a company that maintains a bimonthly updated database of all available listed telephone households in the US, following our previously successful recruitment strategies. A list of households with at least one adult aged 18 to 65 years within a 10-mile radius of UCLA Westwood Campus will be purchased every other month. Age information for each household is based on either known age-related data or a statistical estimate of age, predicted on individual household characteristics and Census demographic information. We have used these lists for our previous telephone survey of community-dwelling older adults (R01AG034588). A letter will be sent to the individuals listed by GENESYS Sampling Systems, briefly describing the study and inviting them to participate in the study. Participants interested in the study will contact the project coordinator by email or phone. All interested participants will then go through a two-step screening procedure, consisting of a structured telephone interview and an in-person screening session. The initial screening process will be completed over the phone by the project coordinator. In addition to the telephone screening, we will use a web survey (<https://tinyurl.com/UCLA-LDEP>). When potential participants type this link on their Internet browser or click the advertisement banner on one of the websites, they will be directed to the web survey. Lastly, we will include a QR code on the flyers to facilitate the enrollment. By scanning the QR code, the prospective participants will be directed to the web survey as a screening procedure. The second screening will be done in person by one of the study physicians ([name] [name], [name], or [name]). Most of the assessment will be conducted by the study physician, especially for medical and psychiatric comorbidities. The other interview components including C-SSRS and SCID will be conducted by the project coordinator and reviewed by the study physician. Participants' eligibility will ultimately be determined by the study physician, based on the results from the blood and urine tests as well as the medical and psychiatric evaluation obtained during the in person screening processes. To maximize the participant retention, they will be regularly contacted by phone throughout the study, especially during the 2-week pretreatment period.

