Pretreatment: Leucine is commercially available in US as dietary supplements. For this study, we will use oral preparation of the pharmaceutical grade leucine (12 g/day in 2 divided doses for 2 weeks; Ajinomoto, Raleigh, NC) mixed with effervescent powder. PO placebo will resemble the compounded mixture of leucine and effervescent powder. Clinical studies of leucine have used doses ranging from 2 to 18 g/day.⁸¹⁻⁸⁷ According to a meta-analysis, the long-term supplementation dose (i.e., 10 days to 6 months) ranged from 2.8 to 16.1 g/day with a weighted mean of 8.5 g/day.³⁰ Caspenson et al. found that leucine 12 g/day for 2 weeks improved muscle protein synthesis with a concomitant increase in phosphorylation of mechanistic target of rapamycin (mTOR) following the stimulus of a meal.⁸⁷ As this above-average dose given for 2 weeks caused increases in post-prandial protein synthesis and mTOR activation, both mechanisms also observed in preclinical studies of leucine after the stimulus of endotoxin,⁸⁸ we will use 12 g/day for 2 weeks. Participants will be given leucine or PO placebo on the day of in-person screening and will take it for 2 weeks including the morning of endotoxin administration, hence a total of 28 doses. At the end of pretreatment, subjects will indicate the presence or absence of a number of possible adverse effects in a questionnaire using a 4-point scale from 'not at all' to 'very often': symptoms include not feeling well, headache, weakness, fatigue, nausea, vomiting, burping, stomachache, bloating, flatulence, constipation, diarrhea, dry mouth, change of taste, cough, skin complaints, muscle pain, weight gain, weight loss, dizziness, sweating, and shaking. The adherence will be assessed using the Patient Adherence Questionnaire (PAQ)⁸⁹ and the count-back method (i.e., counting doses remaining in returned packets)⁹⁰ at the end of the pretreatment (i.e., immediately before endotoxin).

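### The leucine adverse-effect checklist is described once, with no pre-drug administration and no stated collection from early stoppers; repeating it at contacts already planned is a cheap improvement

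*Combined protocol and SAP*

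**What the plan says.** The Pretreatment paragraph of C.2.3 describes one adverse-effect questionnaire: "At the end of pretreatment, subjects will indicate the presence or absence of a number of possible adverse effects in a questionnaire". It lists 22 symptoms on a four-point frequency scale. No recall period, onset date or severity grade is given.

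The next sentence, on adherence, explains its own timing as "at the end of the pretreatment (i.e., immediately before endotoxin". That explanation is attached to the adherence measures, though it is reasonable to read the checklist as falling at the same point.

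C.2.4 sets out what is measured before pretreatment: "During the in-person screening session, the following measures will be assessed: sociodemographic information, sleep", followed by mood and anxiety, cognition, C-reactive protein and kynurenine metabolites. The checklist is not among them. According to C.2.3, study drug is handed out on the day of that same screening visit.

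C.2.2 plans contact in between: "they will be regularly contacted by phone throughout the study, especially during the 2-week pretreatment period". The stated purpose is retention; the content of the calls is not described.

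The safety paragraph of C.2.3 says "Participants will be monitored as per the protocol (see Protections of Human Subjects section". That section is not in the file, and the short summary given in its place concerns the endotoxin session.

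The supplied text does not say how symptoms or reasons are recorded for someone who stops leucine or oral placebo early, and it gives no expected dropout rate.

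**The concern.** Two issues need to be kept apart, because they act in opposite directions on the raw rate.

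1. **Who is asked.** No visit is described between screening and the main session, so completing an end-of-pretreatment checklist appears to depend on getting that far. Symptoms bad enough to make someone stop are the ones most at risk of going unrecorded. If such stops are more common in one oral arm, the comparison between arms shifts as well.

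2. **What the answers mean.** Headache, fatigue, bloating and muscle pain occur in healthy people. Without a record before the first dose, a symptom on the checklist cannot be classed as new, worse or long-standing in the person who reports it.

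The stake is the tolerability evidence that the trial hands on. A.8 says the study will inform the design of future leucine trials, and adds: "Given the minimal adverse effects and the additional benefits such as muscle mass preservation, leucine will be a prime candidate". A reader will look to this trial for data bearing on that premise.

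**Working it through.** The plan gives no figure for tolerability or early stopping, so there is nothing of its own to reproduce here. The one documented input is the size of the oral arms. C.2.1 gives "n₁=35 leucine + endotoxin; n₂=35 PO placebo + endotoxin; n₃=10 leucine + IV placebo; n₄=10 PO placebo + IV placebo", so leucine has 35 + 10 = 45 and oral placebo has 35 + 10 = 45. All rates below are assumptions chosen to show direction and range.

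**Step 1: effect of unasked stoppers on one arm's rate.** Let x of 45 truly have a symptom, and let k of those stop because of it and never be asked. The observed rate is (x − k)/(45 − k).

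| k | x = 9 (20.0%) | x = 14 (31.1%) | x = 18 (40.0%) |
|---|---|---|---|
| 0 | 9/45 = 20.0% | 14/45 = 31.1% | 18/45 = 40.0% |
| 1 | 8/44 = 18.2% | 13/44 = 29.5% | 17/44 = 38.6% |
| 2 | 7/43 = 16.3% | 12/43 = 27.9% | 16/43 = 37.2% |
| 4 | 5/41 = 12.2% | 10/41 = 24.4% | 14/41 = 34.1% |
| 6 | 3/39 = 7.7% | 8/39 = 20.5% | 12/39 = 30.8% |

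With no such stops there is no bias. With four, the rate falls by about 6 to 8 points.

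**Step 2: effect on the arm difference.** Assume true rates of 30% on leucine and 20% on oral placebo (difference +10 points), with a fraction s of an arm stopping for symptoms unasked. The observed rate is (p − s)/(1 − s).

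- 5% in both arms: 0.25/0.95 − 0.15/0.95 = 26.3% − 15.8% = +10.5 points.
- 10% on leucine, 5% on placebo: 0.20/0.90 − 0.15/0.95 = 22.2% − 15.8% = +6.4 points.
- On leucine only: 5% gives 26.3% − 20% = +6.3; 10% gives 22.2% − 20% = +2.2; 15% (about 7 of 45) gives 0.15/0.85 = 17.6%, so −2.4 points.

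Under these assumptions, equal stopping leaves the difference almost unchanged. A material bias needs unequal stopping, and the sign reverses only in the most extreme row.

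**Step 3: precision, for scale.** At 30% against 20% with 45 per arm, the 95% half-width is 1.96 × √[(0.30 × 0.70 + 0.20 × 0.80)/45] = 1.96 × 0.0907 = 17.8 points. The tolerability comparison is imprecise whatever is done about stoppers.

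**Step 4: effect of no baseline.** Assume 20% have the symptom beforehand in both arms, and leucine newly causes it in 10% of the rest. The leucine arm shows 0.20 + 0.80 × 0.10 = 28% and oral placebo shows 20%. The raw leucine rate is inflated by background, while the difference of 8 points correctly equals the share with a new symptom (0.80 × 0.10). What is lost is knowing which individuals make up that 8%.

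**The case against.** A reader might infer that people who stop early never enter the data, so that tolerability will look better than it is. The documents do not support that. C.2.3 speaks of subjects without limiting the checklist to session attenders, and early stopping is simply not addressed. The Protections of Human Subjects section could contain a rule that cannot be seen here. This is a risk that follows from silence.

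Nor do the documents show that the calls have no adverse-effect content, or that problems during home dosing come to light only after two weeks. Regular contact is planned and its content is not described. A 14-day recall period is likewise not stated.

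It would also be wrong to link the missing baseline to the missing stoppers. A missing baseline excludes nobody, and it makes raw leucine rates look worse. The randomised, double-blind oral placebo largely removes background symptoms from the arm comparison.

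The stakes are limited too. Tolerability is not one of the three aims, the primary outcome is the POMS, and the remark in A.8 about minimal adverse effects is background and not a conclusion from this checklist. Finally, repeated prompting might raise reported symptoms or influence self-reported mood. That is a fair caution; the documents give no basis for its size, or for assuming it is equal in the two arms.

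These objections remove the certainty and reduce the weight. They leave standing the single stated administration, its absence from the baseline list, and the lack of any stated route for early stoppers.

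**Conclusion.** The point holds as a cheap improvement to data collection; it does not threaten the primary result. On the supplied text, adverse-effect rates could be understated if only those who reach the session complete the checklist, and the arm comparison could be biased if symptom-related stopping also differs by oral arm. The size cannot be determined from the documents. It is nil with no such stops, and about 6 to 8 points in one arm if four symptomatic participants of 45 are never asked, for assumed true rates of 20% to 40%. Separately, without a pre-drug record, raw rates mix background with new complaints and individual new or worsened symptoms cannot be identified; the comparison with oral placebo is largely protected from this. All of it is conditional on the Protections of Human Subjects section not already providing for early stops.

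**What to change.** In C.2.3 and C.2.4, state that the same checklist is given:

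- at the screening visit, before the first dose;
- on the retention calls already planned during pretreatment;
- by phone when anyone stops early, with the reason for stopping;
- at the end of pretreatment, as now.

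Report new or worsened symptoms, early stops and reasons by oral arm (45 against 45) for all randomised participants. If the Protections of Human Subjects section already covers early stops, a cross-reference in C.2.3 is enough for that part. Particular call days need not be fixed for this to work.

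The cost is a few minutes at each contact and one more table. Prompted questioning may raise reported rates, so the report should say that symptoms were solicited and how often.
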